## 5. Biomarkers are Already a Reality in Health Care

A number of drugs now have biomarker information included in their labels. Biomarker tests are already being used in clinical practice to serve various purposes:

**Predictive biomarkers (efficacy)** – In clinical practice, predictive efficacy biomarkers are used to predict which patients are most likely to respond, or not respond, to a particular drug. Examples include: i) *Her2/neu* overexpression analysis required for prescribing trastuzumab (Herceptin®) to breast cancer patients, ii) *c-kit* expression analysis prior to prescribing imatinib mesylate (Gleevec®) to gastrointestinal stromal tumor patients, and iii) *KRAS* mutational status testing prior to prescribing panitumumab (Vectibix®) or cetuximab (Erbix®) to metastatic colorectal cancer patients.

**Predictive biomarkers (safety)** – In clinical practice, predictive safety biomarkers are used to select the proper drug dose or to evaluate the appropriateness of continued therapy in the event of a safety concern. Examples include: i) monitoring of blood potassium levels in patients receiving drospirenone and ethinyl estradiol (Yasmin®) together with daily long-term drug regimens that may increase serum potassium, and ii) prospective *HLA-B\*5701* screening to identify those at increased risk for hypersensitivity to abacavir (Ziagen®).

**Surrogate biomarkers** – In clinical practice, surrogate biomarkers may be used as alternatives to measures such as survival or irreversible morbidity. Surrogate biomarkers are measures that are reasonably likely, based on epidemiologic, therapeutic, pathophysiologic, or other evidence, to predict clinical benefit. Examples include: i) LDL level as a surrogate for risk of cardiovascular diseases in patients taking lipid-lowering agents such as atorvastatin calcium (Lipitor®), ii) blood glucose as a surrogate for clinical outcomes in patients taking anti-diabetic agents, and iii) HIV plasma viral load and CD4 cell counts as sur-

rogates for time-to-clinical-events and overall survival in patients receiving antiretroviral therapy for HIV disease.

**Prognostic biomarkers** – Biomarkers can also help predict clinical outcomes independent of any treatment modality. Examples of prognostic biomarkers used in clinical practice include: i) CellSearch™ to predict progression-free survival in breast cancer, ii) anti-CCP (cyclic citrullinated protein) for the severity of rheumatoid arthritis, iii) estrogen receptor status for breast cancer, and iv) anti-dsDNA for the severity of systemic lupus erythematosus.

## 6. Biomarker Samples from Clinical Trials: An Invaluable Resource

Adequate sample sizes and high-quality data from controlled clinical trials are key to advancements in biomarker research. Samples collected in clinical trials create the opportunity for investigation of biomarkers related to specific drugs, drug classes, and disease areas. Clinical drug development programs are therefore an invaluable resource and a unique opportunity for highly productive biomarker research. In addition to conducting independent research, pharmaceutical companies are increasingly contributing to consortia efforts by pooling samples, data, and expertise in an effort to conduct rigorous and efficient biomarker research and to maximize the probability of success.

## 7. Informed Consent for Collection & Banking of Biomarker Samples

Collection of biological samples in clinical trials must be undertaken with voluntary informed consent of the participant (or legally-acceptable representative). Policies

and regulations for legally-appropriate informed consent vary on national, state, and local levels, but are generally based on internationally recognized pillars of ethical conduct for research on human subjects.

#### Optional vs. Required Subject Participation

Depending on the relevance of biomarker research to a clinical development program at the time of protocol development, the biomarker research may be a core required component of a trial (e.g., key to elucidating the drug mechanism of action or confirming that the drug is interacting with the target) or may be optional (e.g., to gain valuable knowledge that enhances the understanding of diseases and drugs). Informed consent for the collection of biomarker samples may be presented either in the main clinical informed consent form or as a separate informed consent form, with approaches varying somewhat across pharmaceutical companies. The relevance of biomarker research to a clinical development program may change over time as the science evolves. The samples may therefore increase in value after a protocol is developed.

#### Consent for Future Research Use

[figure not shown]
While it can be a challenge to specify the details of the research that will be conducted in the future, the I-PWG holds the view that future use of samples collected for exploratory biomarker research in clinical trials should be permissible when i) the research is scientifically sound, ii) participants are informed of the scope of the intended future research, even if this is broadly defined (see potential uses in Section 4 above), iii) autonomy is respected by providing the option to consent separately to future use of samples or by providing the option to terminate further use of samples upon request (consent withdrawal / sample destruction), and iv) industry standards for confidentiality protection per Good Clinical Practice guidelines are met. Importantly, any research using banked samples should be consistent with the original informed consent, except where otherwise permitted by local law or regulation.

Important elements of informed consent for **future use** of samples include, but are not limited to:

**The scope of research** – Where the scope of the potential future research is broad, participants should be informed of the boundaries of the research. While it may not be possible to describe the exact analytical techniques that will be used, or specific molecules that will be analyzed, it is possible to clearly articulate in reasonable detail the type of research to be conducted and its purpose. Information regarding whether stored samples may be shared with other parties or utilized for commercialization purposes should also be addressed.

**Withdrawal of consent / sample destruction** – The informed consent form should inform participants of their right to withdraw their consent / request destruction of their samples. This should include the mechanisms for exercising that right and any limitations to exercising that right. For example, participants should be informed that it is not possible to destroy samples that have been anonymized. In addition, according to industry standards and regulatory guidance, participants should be informed that data already generated prior to a consent withdrawal request are to be maintained as part of the study data.

**The duration of storage** – The permissible duration of storage may vary according to the nature and uses of the samples and may also vary on national, state, and local levels. The intended duration of storage, including indefinite storage, should be specified.

## 8. Biomarker Sample Collection in Different Countries

Collection of biological samples for biomarker research is straightforward in most jurisdictions. Some countries have specific laws and regulations regarding collection, labeling, storage, export, and/or use of exploratory samples. In addition, some regulations distinguish between DNA and non-DNA samples or between samples used for diagnostic purposes and samples collected for scientific research. Processes for the collection, labeling, storage, export, and/or use of biomarker samples should always adhere to the laws and regulations of the country/region in which those samples are collected.

## 9. Return of Research Results to Study Participants

Policies for the return of biomarker research results to study participants who request them vary among pharmaceutical companies. There are many considerations that pharmaceutical companies weigh when determining their policy regarding the return of biomarker research results to study participants. These include:

- i) the conditions under which biomarker research results were generated (i.e., exploratory research laboratory versus accredited diagnostic laboratory)
- ii) whether the results will have an impact on the medical care of the participant or on a related person, if applicable
- iii) whether genetic counseling is recommended (for genetic results)
- iv) the ability to accurately link the result to the individual from whom the sample was collected
- v) international, national, and local guidelines, policies, legislation, and regulations regarding participants' rights to access data generated on them

Renegar *et al.* 2008 and Article 29 Data Protection Working Party (an advisory committee to the European Commission on the European Data Protection Directive) have addressed these considerations in detail in relation to pharmacogenomic research data and provided a list of documents addressing the general issue of return of research results.

## 10. Benefits and Risks Associated with Biomarker Research

### Benefits

While it may not always directly benefit the study participant who is providing the samples, biomarker research can improve overall understanding of disease and treatment of future patients receiving therapies developed from such research. Patients are now benefiting from retrospective biomarker research conducted on samples collected from clinical trials and stored for exploratory research. One example is the recent label update to the EGFR antibody drugs cetuximab (Erbix®) and panitumumab (Vectibix®) which highlights the value of *KRAS* status as a predictive biomarker for treatment of metastatic colorectal cancer with this class of drug.

The humanitarian benefit of human research is recognized by the Nuremberg Code. Provided that the degree of risk does not exceed that determined by the humanitarian importance of the problem to be solved, research participants should not be denied the right to contribute to the greater common good.

### Risks

Risks associated with biomarker research are primarily related to the physical aspects of obtaining the sample and to patient privacy concerns.

Physical risks associated with biomarker sample collection in clinical trials can be characterized in two ways:  
i) negligible additional risk when the biomarker sample is collected as part of a procedure conducted to support

other core trial objectives, and ii) some added risk where the sampling procedure would otherwise have not been performed as a core component of a trial. Risks are also determined by the invasiveness of the sample collection procedure.

Privacy risks are generally those associated with the inappropriate disclosure and misuse of data. Pharmaceutical companies have policies and procedures for confidentiality protection to minimize this risk for all data collected and generated in clinical trials. These may vary across companies, but are based on industry standards of confidentiality and privacy protection highlighted in the following section. Importantly, privacy risks inherent to biomarker data are no greater than other data collected in a clinical trial.

## 11. Privacy, Confidentiality, and Patient Rights

Maintaining the privacy of study participants and the confidentiality of information relating to them is of paramount concern to industry researchers, regulators, and patients. Good Clinical Practice (GCP), the standard adhered to in pharmaceutical clinical research, is a standard that

*"...provides assurance that the data and reported results are credible and accurate, and that the rights, integrity, and confidentiality of trial subjects are protected",*

where confidentiality is defined as, *"The prevention of disclosure, to other than authorized individuals, of a sponsor's proprietary information or of a subject's identity."*

This standard dictates that *"the confidentiality of records that could identify subjects should be protected, respecting the privacy and confidentiality rules in accordance with applicable regulatory requirements."*

Exploratory biomarker research in pharmaceutical development is commonly conducted in research laboratories that are not accredited to perform diagnostic tests used for healthcare decision-making. Therefore, results from exploratory biomarker research usually are not appropriate for use in making decisions about a trial participant's health. In addition, exploratory research data should not be included as part of a participant's medical record accessible for use by insurance companies. Legislation and policies to protect individuals against discrimination based on genetic information continually evolve based on social, ethical, and legal considerations. Examples of such legislation include the Human Tissue Act 2004 (UK) and the Genetic Information Nondiscrimination Act (GINA) 2008 (USA).

## 12. Where to Get More Information?

Educational resources related to biomarker and pharmacogenomic research that caters to health care professionals, IRBs/IECs, scientists, and patients are continually being created and are publicly available. Links to many of these resources are available through the I-PWG website: [www.i-pwg.org](http://www.i-pwg.org).

## 13. What is I-PWG?

The Industry Pharmacogenomics Working Group (I-PWG) (formerly the Pharmacogenetics Working Group) is a voluntary association of pharmaceutical companies engaged in pharmacogenomic research. The Group's activities focus on non-competitive educational, informational, ethical, legal, and regulatory topics. The Group provides information and expert opinions on these topics and sponsors educational/informational programs to promote better understanding of pharmacogenomic and other biomarker research for key stakeholders. The I-PWG interacts with regulatory author-

ities and policy groups to ensure alignment. More information about the I-PWG is available at: [www.i-pwg.org](http://www.i-pwg.org).

## 12.4 ECOG Performance Status

ECOG	Characteristics
0	Normal activity. Fully active, able to carry on all pre-disease performance without restriction.
1	Symptoms, but ambulatory. Restricted in physically strenuous activity, but ambulatory and able to carry out work of a light or sedentary nature (e.g., light housework, office work).
2	In bed <50% of the time. Ambulatory and capable of all self-care, but unable to carry out any work activities. Up and about more than 50% of waking hours.
3	In bed >50% of the time. Capable of only limited self-care, confined to bed or chair more than 50% of waking hours.
4	100% bedridden. Completely disabled. Cannot carry on any self-care. Totally confined to bed or chair.
5	Dead

\* As published in Am. J. Clin. Oncol.: Oken, M.M., Creech, R.H., Tormey, D.C., Horton, J., Davis, T.E., McFadden, E.T., Carbone, P.P.: Toxicity And Response Criteria Of The Eastern Cooperative Oncology Group. Am J Clin Oncol 5:649-655, 1982. The Eastern Cooperative Oncology Group, Robert Comis M.D., Group Chair

## 12.5 Calculation of Renal Clearance

Subjects aged < 65 years: **Cockroft &Gault** formula

$$\text{Male} = 1.25 \times \text{weight (kg)} \times (140 - \text{age}) / \text{serum creatinine } (\mu\text{mol/L})$$

$$\text{Female} = 1.04 \times \text{weight (kg)} \times (140 - \text{age}) / \text{serum creatinine } (\mu\text{mol/L})$$

Subjects aged  $\geq$  65 years: **MDRD** (Modification of Diet in Renal Disease) formula

$$\text{Male} = 186 \times (\text{serum creatinine } (\mu\text{mol/L}) \times 0,0113)^{-1,154} \times \text{age}^{-0,203}$$

x 1,21 in subjects with black skin

x 0.742 in female

**Clearance can be calculated using tools available via the internet, e.g.**

[http://filfol.fr/medecine/cockroft\\_MDRD.html](http://filfol.fr/medecine/cockroft_MDRD.html)

or

<http://mdrd.com/>

## 12.6 Non-Exhaustive List of Drugs and Substances with the Potential to Interfere with CYP3A4 and CYP2A6

**Strong CYP3A4 interfering agents are prohibited (in bold and underlined).**

A **strong inhibitor** increases the AUC of a substrate for a given CYP by  $\geq 5$ -fold or  $> 80\%$  decrease in clearance. A **strong inducer** decreases the AUC of a substrate for a given CYP by  $\geq 80\%$ .

Strong CYP3A4 inducers	Strong CYP3A4 inhibitors		Moderate CYP3A4 inducers	Moderate CYP3A4 inhibitors	
avasimibe carbamazepine phenytoin rifampicin St John's wort 	boceprevir clarithromycin conivaptan grapefruit juice  indinavir itraconazole ketoconazole lopinavir mibefradil	nefazodone nelfinavir posaconazole ritonavir saquinavir telaprevir telithromycin tipranavir voriconazole	amobarbital dexamethasone efavirenz felbamate nevirapine omeprazole phenobarbital pioglitazone primidone rifabutin tamoxifen troglitazone	atazanavir amiodarone amprenavir aprepitant cimetidine cyclosporine darunavir delavirdine diltiazem erythromycin	fluconazole fosamprenavir imatinib miconazole suboxone verapamil
CYP3A Sensitive substrates				CYP3A Substrates with a Narrow Therapeutic Range	
alfentanil	dronedarone	lovastatin	simvastatin	alfentanil	fentanyl
aprepitant	eletriptan,	lurasidone	sirolimus	astemizole	pimozide
budesonide	eplerenone,	maraviroc	tolvaptan	cisapride	quinidine
buspirone	everolimus	midazolam	tipranavir	cyclosporine	sirolimus
conivaptan	felodipine	nisoldipine	triazolam	dihydroergotamine	tacrolimus
darifenacin	indinavir	quetiapine	vardenafil	ergotamine	terfenadine
darunavir	fluticasone	saquinavir			
dasatinib	lopinavir	sildenafil			
CYP2A6 inducers	CYP2A6 inhibitors		Other CYP2A6 substrates		
phenobarbital rifampicin	grapefruit juice ketoconazole methoxsalen pilocarpine tranlycypromine		coumarin halothane losigamone methoxyflurane	nicotine quinoline SM-12502 valproic acid	

1. Preparation-dependent

## **12.7 Guidance for Potential Drug-Induced Liver Injury (DILI)**

### **12.7.1 Purpose**

The purpose of this document is to provide guidance to enable the investigator/study coordinator to provide clinical follow-up and systematically gather and report data on potential DILI. The data collected will be used by the Sponsor to create narratives for regulatory agency reporting.

### **12.7.2 Introduction**

Hepatotoxicity is injury or damage to the liver that may be associated with impaired liver function [1]. Drug-induced hepatotoxicity is one of the most common causes of termination of drug development, a major reason for refusal of market authorization and for restricted use, and the single most important cause of the withdrawal of market authorization for products [2]. Thus, drug-induced hepatotoxicity is a major concern during the discovery, development to post-authorization phases of the product life cycle (excerpted from Draft Guidance Document, Hepatotoxicity of Health Products, Ministry of Public Health, Canada, December 2010)[3].

As stated in the United States Food and Drug Administration (FDA) “Guidance for Industry - Drug-Induced Liver Injury: Premarketing Clinical Evaluation” [4]; hepatocellular injury (usually detected by serum aminotransferase elevations [AT]) can be caused by drugs that rarely, if ever, cause severe DILI (e.g., aspirin, tacrine, statins, and heparin), as well as by drugs that do cause such injury. The frequency of serum AT elevations also is not a good indicator of a potential for severe DILI because drugs such as tacrine (not a cause of severe DILI) can cause AT elevations in as many as 50 percent of patients. Very high levels of observed ATs may be a somewhat better indicator of potential for severe DILI, but the most specific indicator is evidence of altered liver function accompanying or promptly following evidence of hepatocellular injury.

The single clearest (most specific) predictor found to date of a drug’s potential for severe hepatotoxicity, is the occurrence of hepatocellular injury (AT elevation) accompanied by increased serum total bilirubin (TBL) not explained by any other cause, such as viral hepatitis or exposure to other hepatotoxins, and without evidence of cholestasis, together with an increased incidence of AT elevations in the overall trial population compared to control. Increased plasma prothrombin time, or its international normalized ratio (INR), a consequence of reduced hepatic production of Vitamin K-dependent clotting factors, is another potentially useful measure of liver function that might suggest the potential for severe liver injury.

Recognition of the importance of altered liver function, in addition to liver injury, began with Hyman Zimmerman's observation that drug-induced hepatocellular injury (i.e., AT elevation) accompanied by jaundice (i.e., TBL elevation) had a poor prognosis, with a 10 to 50 percent mortality from acute liver failure (in pretransplantation days) [5][6]. This became known as "Hy's Law". This document describes the recommended process for monitoring and evaluation of subjects meeting the laboratory criteria for potential DILI defined as:

- an elevated alanine transaminase (ALT) or aspartate transaminase (AST) lab value that is greater than or equal to three times (3X) the upper limit of normal (ULN) and
- an elevated TBL lab value that is greater than or equal to two times (2X) ULN and
- at the same time, an alkaline phosphatase (ALP) lab value that is less than 2X ULN,

as a result of within-protocol-specific testing or unscheduled testing.

The protocol identifies these laboratory criteria for potential DILI as ECIs. ECIs are selected adverse experiences that must be reported to the Sponsor within 24 hours. The Principal Investigator should record these ECIs on the Adverse Experience Case Report Forms (CRFs) and complete pertinent adverse experience fields as outlined in the Data Entry Guidelines (DEGs).

### **12.7.3 Close Observation Recommendations**

The following steps should be taken when a subject is observed to have an elevated AST or ALT lab value that is greater than or equal to 3X ULN and an elevated TBL lab value that is greater than or equal to 2X ULN and, at the same time, an ALP lab value that is less than 2X ULN, as a result of within-protocol-specific testing or unscheduled testing. In addition, close monitoring of *isolated* bilirubin increases greater than 2X ULN will be required.

Initiate **close observation**, defined below, and continue performing **follow-up to resolution**.

**Close observation is defined as follows:**

- Repeat liver enzyme and serum bilirubin tests two (2) or three (3) times weekly. Frequency of retesting can decrease to once a week or less if abnormalities stabilize or study drug has been discontinued and the subject is asymptomatic.
  - For subjects with *isolated* bilirubin elevations greater than 2X ULN, repeat serum bilirubin tests every 2 weeks until the bilirubin returns to normal or baseline.
- Obtain a more detailed history of symptoms and prior or concurrent diseases. (See Section 12.7.5).
- Obtain a history of concomitant medication use (including prescription and nonprescription medications, herbal and other dietary supplements), alcohol use, recreational drug use and special diets. (See Section 12.7.5 for details.)
- Obtain a history of exposure to chemical agents or other environmental toxins.

- Obtain additional history and complete Stage 1 work-up to attempt to rule out other potential causes of the transaminase elevation, including but not limited to the following: acute viral hepatitis types A, B, C, D, and E; autoimmune or alcoholic hepatitis; non-alcoholic steatohepatitis (NASH); hypoxic/ischemic hepatopathy; and biliary tract disease. (See Section 12.7.5.5 for details.)
- Consider gastroenterology or hepatology consultation.

**In general, treatment with study therapy should be stopped if the laboratory criteria for potential DILI are met. Please refer to the specific discontinuation criteria in the protocol as appropriate.**

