### 5.2.1.6 Dose Adaptation

The Common Terminology Criteria for Adverse Events version 4.0 (CTCAE 4.0) must be used to grade the severity of adverse events. MK-8628 will be withheld for drug related Grade 4 hematologic toxicities, non-hematological toxicity  $\geq$  Grade 3 including laboratory abnormalities, and severe or life-threatening AEs as per [Table 7](#) below. If a dose of MK-8628 is withheld for toxicity, then subjects may resume dosing with MK-8628 if that is appropriate at their next scheduled appointment or when toxicity has improved as described below.

Table 7: Dose Modification Guidelines for Drug-Related Adverse Events

Toxicity	Grade	Hold Treatment (Y/N)	Timing for restarting treatment	Dose/Schedule for restarting treatment	Criteria for discontinuation after consultation with Sponsor
Hematologic toxicity	1, 2	No	N/A	N/A	N/A
	3 associated neutropenia with infection; or thrombocytopenia with bleeding or lasting > 7 days	Yes	Toxicity resolves to Grade 0-1, or to baseline	Resume treatment at next lower dose level ( Table 8 )	Toxicity does not resolve within 2 weeks of last dose. Permanent discontinuation should be considered for any severe or life-threatening event
	4 or febrile neutropenia	Yes	Toxicity resolves to Grade 0-1, or to baseline	Resume treatment at next lower dose level ( Table 8 )	Toxicity does not resolve within 2 weeks of last dose. Permanent discontinuation should be considered for any severe or life-threatening event
Non-Hematologic	1, 2	No	N/A	N/A	N/A

Toxicity	Grade	Hold Treatment (Y/N)	Timing for restarting treatment	Dose/Schedule for restarting treatment	Criteria for discontinuation after consultation with Sponsor
Laboratory Abnormalities	3, 4  With or without symptoms lasting > 48 hours	Consider holding  Hold treatment for total bilirubin increases >2X ULN or 2X baseline (if elevated at baseline) and/or AST or ALT ≥ 5X ULN	Toxicity resolves to Grade 0-1, or to baseline	Laboratory abnormalities resolve within 1 week: treat at same dose and schedule  Laboratory abnormalities do not resolve within 1 week: may consider resuming treatment at next lower dose level (Table 8)	Toxicity does not resolve within 2 weeks of last dose. Permanent discontinuation should be considered for any severe or life-threatening event
Non-Hematologic toxicity	1 2	No	N/A	N/A	N/A

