### **5.6.1.2 Hepatic Laboratory Abnormalities**

All trial subjects with liver test abnormalities should be monitored weekly until all abnormalities return to normal or to the baseline state. For subjects with isolated total bilirubin increases >2X ULN or 2X baseline (if elevated at baseline), monitoring should be every 2 weeks until bilirubin returns to normal or to the baseline state. Drug induced liver injury (DILI) may develop or progress even after the causative drug has been stopped. Results should be recorded on the case report form and in the database. See Section 12.7 for guidelines on the handling of these events (potential Hy's law cases).

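### For a subject meeting the potential-DILI laboratory criteria, Section 12.7.3, Table 7, the sentence after Table 7 and Section 5.8 do not give one rule on stopping and re-exposure

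*Combined protocol and SAP*

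**What the plan says.** Section 12.7.2 defines the pattern, and Section 7.2.3.2 makes it an event of clinical interest. Four places then bear on what happens to treatment.

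- **Section 12.7.3:** "In general, treatment with study therapy should be stopped if the laboratory criteria for potential DILI are met". The next sentence reads: "Please refer to the specific discontinuation criteria in the protocol as appropriate".
- **Section 5.8**, which lists the reasons for definitive discontinuation, has no liver item. The nearest are unacceptable toxicity, interruption beyond 2 weeks for toxicity, and a DLT that recurs after the dose has been reduced.
- **Table 7**, row for Grade 3 and 4 non-hematologic laboratory abnormalities: "Hold treatment for total bilirubin increases >2X ULN or 2X baseline (if elevated at baseline) and/or AST or ALT ≥ 5X ULN". Treatment may restart at Grade 0-1 or baseline, and on dose the row says: "Laboratory abnormalities resolve within 1 week: treat at same dose and schedule". If resolution takes longer than 1 week, the next lower level may be considered. The row's last column names failure to resolve within 2 weeks of the last dose, and adds: "Permanent discontinuation should be considered for any severe or life-threatening event".
- **The sentence after Table 7** says that once toxicity has recovered, dosing restarts at the next lower level. It makes no exception for the laboratory row.

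Section 5.2.1.4 also counts ALT or AST >3X ULN with bilirubin >2X ULN as a DLT in Part A Cycle 1 if judged drug-related. Section 5.2.1.6 applies the same dose-modification guidance to Part B.

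**The concern.** Section 12.7.2 places aminotransferase elevation with an unexplained bilirubin rise and no cholestasis at the center of its best available warning of severe hepatotoxicity. Here an investigator most needs a single instruction on whether, and at what dose, the subject may be exposed again. The plan instead leaves the answer to whichever section is opened first, in a trial with at least nine centers.

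Subject safety is the main stake. Divergent handling would also feed into discontinuations due to AEs and dose adaptations due to AEs (both endpoints in Section 8.4.1), into extent of exposure (Section 8.12), and through them into the safety and tolerability part of the RP2D decision (Section 5.2.1.5).

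**Working it through.** The point rests on no sample size, power or event count, so the check is a comparison of texts.

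**Test case.** Take a Part A subject in Cycle 1 with ALT >3X ULN, bilirubin >2X ULN and alkaline phosphatase <2X ULN, judged drug-related, whose values return to Grade 0-1 or baseline within 1 week.

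| Place | What it supports for this subject |
|---|---|
| 12.7.3 | Stop, as a general rule; then see the discontinuation criteria |
| 5.8 | No liver criterion; an investigator could invoke unacceptable toxicity, which is not defined for this pattern |
| Table 7, laboratory row | Hold, then restart at the same dose and schedule |
| Sentence after Table 7 | Restart at the next lower dose level |

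1. **The deferral does not settle the matter.** Section 12.7.3 hands the decision to the protocol's criteria. Section 5.8 has nothing liver-specific. Table 7 has a discontinuation column, but its entry for this row does not mention the combined pattern and leaves early permanent discontinuation as something to consider.

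2. **Table 7 and the text beneath it disagree on dose.** Same dose and next lower dose cannot both apply to a laboratory abnormality that resolves within 1 week. This holds for any abnormality in that row; it matters most for the potential-DILI pattern.

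3. **The same-dose path sits badly with the DLT rules.** The test subject has had a DLT under Section 5.2.1.4. Section 5.8 and the Trial Summary discontinue for a DLT that recurs despite a dose reduction, which presupposes a reduction after the first. Table 7's same-dose path involves none.

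4. **Part B adds a gap.** The note under Table 8 allows interruption only at 10 mg BID. For subjects at that dose the next-lower-level sentence cannot be followed, so the possible courses are stopping or a same-dose restart.

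The result is three courses for the test subject: stopped, restarted at the same dose, or restarted at a lower dose.

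**The case against.** The strongest reply is that these texts form a hierarchy. Section 12.7.3 is a recommendation, qualified as general, and yields to the protocol body. It does not call the stop permanent, and Section 12.7.5.1 asks whether the drug was interrupted or the subject re-challenged, so a hold followed by a restart is foreseen. Resumption under Section 5.2.1.6 is permissive. Table 7 has its own discontinuation column. Table 12 requires advance sponsor approval for rechallenge after a serious event that the drug may have caused, or where re-exposure carries significant added risk.

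Much of this stands. A reader might infer that Table 7 compels re-exposure while Section 12.7.3 forbids it, so that sites would act in opposite ways. The documents do not support that: a restart may happen, it is not automatic, and for bilirubin >2X ULN with a normal baseline both texts interrupt dosing at the event.

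The reply does not remove the inconsistency. Yielding to the protocol body would suffice if the body held one rule for this pattern; it holds two on restart dose and none specific to the pattern on discontinuation. Permissive wording leaves the choice to each investigator. Table 12's approval step refers back to the dose-modification guidelines, which are the text in conflict, and events of clinical interest include non-serious events.

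A reader might also infer that retest frequencies conflict. Section 5.6.1.2 says: "All trial subjects with liver test abnormalities should be monitored weekly until all abnormalities return to normal or to the baseline state". Section 12.7.3 says: "Repeat liver enzyme and serum bilirubin tests two (2) or three (3) times weekly". This is a general rule beside a specific one: Section 5.6.1.2 sends potential Hy's law cases to Section 12.7, Section 12.7.3 lets the frequency fall to weekly or less later, and both give every 2 weeks for isolated bilirubin elevation.

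Figure 5, the hepatic flow chart, is not reproduced in the text available and could bear on this. Its absence counts neither way.

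**Conclusion.** The inconsistency is real and should be corrected. It is an internal inconsistency, not a design choice: the same subject may be stopped, restarted unreduced or restarted reduced, each with textual support, and the pattern is a DLT in Part A Cycle 1 when drug-related.

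No frequency can be attached to it. The previous solid-tumor study, MK-8628-P003, reported one Grade 3 hyperbilirubinemia/transaminitis DLT among 16 subjects on 80 mg QD continuous dosing (Section 4.1.3). A reader might scale that to the 72 subjects planned here. The documents do not support doing so. They give no ULN multiples or alkaline phosphatase for that event, so nothing shows that it met the potential-DILI criteria. The regimen was different, and the same-dose path also needs resolution within 1 week.

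Nor should the effect on the primary endpoint be overstated. A drug-related case above the DLT thresholds in Part A Cycle 1 counts once in the DLT rate however later dosing is handled. The consequence lies in subject safety and in the exposure, dose-adaptation and discontinuation data.

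The conclusion assumes that Figure 5 does not itself set a single rule on stopping and restart.

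**What to change.** Reconcile Section 12.7.3, the Table 7 laboratory row, the sentence after Table 7 and Section 5.8 so that one rule on stopping and re-exposure applies to the potential-DILI pattern. Specifically:

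- Give the pattern its own entry in Table 7, or a cross-reference there to Section 12.7.
- Make the sentence after Table 7 agree with the restart column, including for subjects at 10 mg BID.
- Name the criterion that Section 12.7.3 points to, and list it in Section 5.8 if it is meant to be a reason for discontinuation.
- State how the rule fits with the pattern being a DLT under Section 5.2.1.4.
- Check that Figure 5 says the same.

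In Section 5.6.1.2, at most make the existing pointer to Section 12.7 explicit about retest frequency.

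Which rule is right is for the sponsor's medical team; this review takes no view. The cost is protocol wording, with no new procedures and no change to sample size or analysis.
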